STUDY PROTOCOL AND STATISTICAL ANALYSIS PLAN

NCT02350127

Preventing Loss of Independence through Exercise (PLIÉ) in Persons with Dementia

Version 1.34

Approved September 10, 2019

TABLE OF CONTENTS

Background Information and List of Protocol Changes	3
Final Study Protocol (V1.34, approved September 10, 2019)	
Study Design, Section 11.1	17
Hypotheses and Specific Aims, Sections 12.1 and 12.2	18
Statistical Analysis Plan, Section 12.3	18
Background and Preliminary Studies, Sections 13.1 and 13.2	19
Inclusion/Exclusion Criteria, Sections 14.6 and 14.7	21
Procedures, Section 16.1	23
Data and Safety Monitoring Plan (V1.1, Sections 18.0 and 19.0, approved 11/20/2014)	41

Background Information

The University of California San Francisco (UCSF) Institutional Review Board (IRB) Study Application was used as the Study Protocol of Record for this study. The IRB-approved Study Application includes information about the overall study design, specific aims and hypotheses, statistical analysis plan, inclusion/exclusion criteria, study methods and procedures, and data and safety monitoring plan. The Study Application was originally approved by the UCSF IRB on November 20, 2014 (V1.1). Protocol changes made prior to study initiation and after study initiation are summarized in the table below. The most recently approved version of the Study Application (V1.34, approved September 10, 2019) is included here along with the Data and Safety Monitoring Plan from the originally approved version (V1.1, approved November 20, 2014).

List of Protocol Changes

Changes made prior to study initiation	Version Number	Date approved
Study design: changed from 12-month parallel-group randomized, controlled trial (RCT) with 6-month intervention and 6-month follow-up periods (assessments at baseline, 6 months, 12 months) to 8-month waitlist RCT with 4-month immediate start and 4-month delayed start groups (assessments at baseline, 4 months, 8 months)	V1.4	5/19/2015
Sample size: changed from 16/site, 9 sites (n=144) to 20/site, 6 sites (n=120)	V1.4	5/19/2015
Eligibility criteria: expanded to include diagnoses of memory loss as well as dementia; restricted severity to mild-to-moderate (Clinical Dementia Rating [CDR] 1 or 2); expanded to include veterans and non-veterans in the community	V1.4	5/19/2015
Outcome measures: Added Falls Efficacy Scale; added Positive Aspects of Caregiving Scale; replaced Functional Independence Measure with Disability Assessment for Dementia	V1.4	5/19/2015
Changes made after study initiation	Version Number	Date approved
Eligibility criteria: expanded to include mild cognitive impairment diagnosis or CDR 0.5	V1.10	1/13/2016
Outcome measures: Anonymous satisfaction survey added	V1.16	7/18/2016
Outcome measures: Added Perceived Stress Scale and open-ended questions about impact of California wildfires.	V1.27	11/21/2017

Study Application (Version 1.34)

1.0 General Information

***Enter the full title of your study:**

Preventing Loss of Independence through Exercise (PLIE) in Persons with Dementia

***Enter the study number or study alias**

PLIE-VA

* This field allows you to enter an abbreviated version of the Study Title to quickly identify this study.

5.0 Initial Screening Questions - Updated 9/13

(Note: You must answer every question on this page to proceed).

If you are converting to the new form, check questions 5.4, 5.6, 5.7, 5.8 and 5.10 before saving and continuing to the next section.

5.1 * Application type:

- Full Committee
- Expedited
- Exempt

5.2 * Risk level (Help Text updated 9/13):

- Minimal risk
- Greater than minimal risk

5.3 * Subject contact:

- Yes (including phone, email or web contact)
- No (limited to medical records review, biological specimen analysis, and/or data analysis)

5.4 * Funding (past or present):

- Funded or will be funded (external sponsor, gift, program or specific internal or departmental funds)
- Unfunded (no specific funds earmarked for this project)
- Unfunded student project

5.5 * The Principal Investigator and/or one or more of the key study personnel has financial interests related to this study:

Yes No

If **Yes**, the Conflict of Interest Advisory Committee (COIAC) office may contact you for additional information.

5.6 * This is an investigator-initiated study:

Yes No

5.7 * This study ONLY involves retrospective records review and/or identifiable biospecimen analysis:

Yes No

5.8 * This is a clinical trial:

Yes No

Clinical Trial Registration

"NCT" number for this trial:

NCT02350127

5.9 * This is a multicenter study:

Yes No

5.10 * This application involves the study of unapproved or approved drugs, devices, biologics or in vitro diagnostics:

Yes No

5.11 * This application involves a Humanitarian Use Device:

- No
 Yes, and it includes a research component
 Yes, and it involves clinical care ONLY

5.12 * This study involves human stem cells (including iPS cells and adult stem cells), gametes or embryos:

- No
 Yes, and requires CHR and GESCR review
 Yes, and requires GESCR review, but NOT CHR review

5.13 * This is a CIRB study (e.g. the NCI CIRB will be the IRB of record):

Yes No

5.14 * This application includes a request to rely on another IRB (other than NCI CIRB):

Yes No

Note: If this request is approved, the CHR will **NOT** review and approve this study. Another institution will be the IRB of record.

6.0 Expedited Review Categories

6.1 * If you think this study qualifies for expedited review, select the regulatory category(ies) that the research falls under:

- Category 1: A very limited number of studies of approved drugs and devices
- Category 2: Blood sampling
- Category 3: Noninvasive specimen collection (e.g. buccal swabs, urine, hair and nail clippings, etc.)
- Category 4: Noninvasive clinical procedures (e.g. physical sensors such as pulse oximeters, MRI, EKG, EEG, ultrasound, moderate exercise testing, etc.)
- Category 5: Research involving materials (data, documents, records, or specimens) that were previously collected for either nonresearch or research purposes
- Category 6: Use of recordings (voice, video, digital or image)
- Category 7: Low risk behavioral research or research employing survey, interview, oral history, focus group, program evaluation, human factors evaluation, or quality assurance methodologies

7.0 Funding

7.1 Identify all sponsors and provide the funding details. If funding comes from a Subcontract, please list only the Prime Sponsor: Note: we require only a P Number OR an A Number for funding coming through UCSF. Please avoid these common errors in funding documentation:

- **DO NOT add the A Number if a P Number was already provided OR update the A Number field when a new funding cycle begins. The IRB does NOT use this information or want these changes made.**
- **DO NOT add a grant continuation as a new funding source.**

External Sponsor:

View Details	Sponsor Name	Sponsor Type	Awardee Institution	Contract Type:	UCSF RAS "P" number or eProposal number	UCSF RAS System Award Number ("A" + 6 digits)
	US Dept of Defense	01	NCIRE	Grant		
Sponsor Name:		US Dept of Defense				
Sponsor Type:		01				
Sponsor Role:		Funding Monitoring				
CFDA Number:						
Grant/Contract Number:		AZ160019				
Awardee Institution:		NCIRE				

Is Institution the Primary Grant Holder:	Yes
Contract Type:	Grant
UCSF RAS "P number" or eProposal number:	
UCSF RAS System Award Number ("A" + 6 digits):	
Grant Number for Studies Not Funded thru UCSF:	
Grant Title:	
PI Name: (If PI is not the same as identified on the study.)	
Significant Discrepancy:	

US Dept of Veterans Affairs 01

SF VAMC Research Office

Grant

Sponsor Name:	US Dept of Veterans Affairs
Sponsor Type:	01
Sponsor Role:	Funding
CFDA Number:	
Grant/Contract Number:	TBD
Awardee Institution:	SF VAMC Research Office
Is Institution the Primary Grant Holder:	Yes
Contract Type:	Grant
UCSF RAS "P number" or eProposal number:	
UCSF RAS System Award Number ("A" + 6 digits):	
Grant Number for Studies Not Funded thru UCSF:	
Grant Title:	
PI Name: (If PI is not the same as identified on the study.)	
Significant Discrepancy:	

Gift, Program, or Internal Funding (check all that apply):

- Funded by gift (specify source below)
- Funded by UCSF or UC-wide program (specify source below)
- Specific departmental funding (specify source below, if applicable)

List the gift, program, or departmental funding source:

7.2 If you tried to add a sponsor in the question above and it was not in the list, follow these steps:

- **If funding has already been awarded or the contract is being processed by the Office of Sponsored Research (OSR) or Industry Contracts Division (ICD), your sponsor is already in the system and the project has an eProposal Proposal or Award number. Check with your**

department's OSR Staff or ICD Officer to ask how the sponsor is listed in the UC sponsor list and what the Proposal or Award number is. Click here to find your OSR staff and here to find your ICD staff.

- If your sponsor is not yet in the list, enter it in the box below.

Sponsor not in list

Only if your sponsor is not yet in the list, type the sponsor's name:

If the funding is administered by the UCSF Office of Sponsored Research, your study will not receive CHR approval until the sponsor and funding details have been added to your application.

7.3 * This study is currently supported in whole or in part by Federal funding OR has received ANY Federal funding in the past (Help Text updated 9/13):

Yes No

If **yes**, indicate which portion of your grant you will be attaching:

- The Research Plan, including the Human Subjects Section of your NIH grant or subcontract
- For other federal proposals (contracts or grants), the section of the proposal describing human subjects work
- The section of your progress report if it provides the most current information about your human subjects work
- The grant is not attached. The study is funded by an award that does not describe specific plans for human subjects, such as career development awards (K awards), cooperative agreements, program projects, and training grants (T32 awards) OR UCSF (or the affiliate institution) is not the prime recipient of the award

9.0 Studies Involving Other Sites

9.1 UCSF is the coordinating center:

Yes No

If **Yes**, describe the plan for communicating safety updates, interim results, and other information that may impact risks to the subject or others among sites:

If **Yes**, describe the plan for sharing modification(s) to the protocol or consent document(s) among sites:

9.2 Check any other UC campuses with which you are collaborating on this research study:

- UC Berkeley
- UC Davis
- Lawrence Berkeley National Laboratory (LBNL)
- UC Irvine
- UC Los Angeles
- UC Merced
- UC Riverside
- UC San Diego
- UC Santa Barbara
- UC Santa Cruz

9.3 Are the above UC campuses requesting to rely on UCSF's IRB (check all that apply):

- Yes (Submit a reliance request through the UC IRB Reliance Registry)
- No (Complete IRB Approval Certification section)

*** The research at this site will be reviewed by:**

- The non-affiliated site's IRB or a private IRB
- The non-affiliated site is requesting UCSF to be the IRB of record for this study
- The non-affiliated site is not engaged in the human subjects research and has provided a letter of support

If the other site's IRB approval letter is available now, attach it to the application. If the IRB approval letter is not yet available, submit it once you receive it.

Or, if the other site is **not engaged** in human subjects research, attach the letter of support to your application.

11.0 Study Design

11.1 * Study design (Help Text updated 9/13):

We propose to test the efficacy of the Preventing Loss of Independence through Exercise (PLIÉ) program by performing a randomized, controlled trial (RCT) at adult day health centers that have current contracts with the San Francisco Veterans Affairs Medical Center (SFVA) or other local VA facilities. We propose to enroll participants in cohorts of 20 at a given center at a time and randomize them in blocks to Group 1 (n=10) or Group 2 (n=10) using a waitlist design. Veterans will be prioritized for enrollment. Study participants randomized to Group 1 will participate in the PLIÉ program at least 2 days/week, 1 hour/day for a 4-month intervention period while study participants randomized to Group 2 will engage in usual activities. After 4 months, Group 1 will 'graduate' and will be encouraged to engage in maintenance activities while Group 2 participates in PLIÉ at least 2 days/week, 1 hour/day for 4 months. Outcomes and potential mediators will be assessed in all study participants at baseline, 4 and 8 months to examine the effect of the intervention in both groups as well as maintenance of intervention effects post-intervention in Group 1. Study sites will include: Marin Adult Day Health Center in Novato, CA; Institute on Aging, San Francisco, CA; Catholic Charities, Santa Rosa, CA; and Alzheimer's Services of the East Bay, Oakland, CA. Other study sites will be added to the protocol over time.

11.2 If this is a clinical trial, check the applicable phase(s) (Help Text updated 9/13):

- Phase I
- Phase II
- Phase III
- Phase IV

12.0 Scientific Considerations

12.1 Hypothesis (Help Text updated 9/13):

This study has a hypothesis:

Yes No

If yes, state the hypothesis or hypotheses:

1. Study participants will experience significantly greater improvements on the co-primary outcomes of cognitive function (Alzheimer's Disease Assessment Scale-cognitive subscale, ADAS-cog), physical performance (Short Physical Performance Battery, SPPB) and quality of life (Quality of Life in Alzheimer's Disease, QOL-AD) when participating in PLIÉ versus Usual Care (UC).
2. Caregivers will experience significantly greater reductions in caregiver burden (Caregiver Burden Inventory, CBI) and improvements in positive feelings about caregiving (Positive Aspects of Caregiving, PAC) when participating in PLIÉ versus UC.
3. The benefits of PLIÉ on participant and caregiver outcomes will be maintained from 4 to 8 months in Group 1.

12.2 * List the specific aims:

Aim 1. To determine whether PLIÉ improves participant outcomes over 4 months compared to Usual Care (UC).

Aim 2. To determine whether PLIÉ improves caregiver outcomes over 4 months compared to UC.

Aim 3. To determine whether the effects of PLIÉ are maintained over 4 months post-intervention.

12.3 Statistical analysis:

All primary analyses will be performed using intent-to-treat principles. All variables will first be assessed for evidence of outlier values or skewed distributions. Baseline characteristics and potential confounders will be summarized for participants randomized to Group 1 versus Group 2 using standard methods such as means/standard deviations and medians/inter-quartile ranges for continuous variables and frequencies with percentages for categorical variables. Differences between the groups at baseline will be statistically tested using t-tests for continuous variables or non-parametric alternatives as indicated and Chi-square tests for categorical variables. Any differences detected will be adjusted for in multivariable models. Our primary analytic approach will be mixed effects linear regression which will enable efficient estimation of treatment effects, inclusion of all study participants in intent-to-treat analyses, and the same analytic approach to be used for all three Aims. Analyses will focus on differences in outcomes when participating in PLIE vs. UC. Fixed effects terms will be included for treatment (PLIE vs. UC), sequence (Group 1 vs. Group 2), time (baseline, 4 months, 8 months) and the interaction between treatment*time. Subjects will be modeled as random effects. Models also will adjust for any baseline differences in demographic factors or confounders that may occur due to chance. Covariates will be included to adjust for any co-interventions that occur (e.g., medication changes), and sensitivity analyses will be performed excluding participants who experience co-interventions. Standard diagnostic tests will be performed to examine model assumptions and distributions of residual values and to assess for potential leverage and influence points. To minimize the risk of Type I error due to multiple comparisons with co-primary outcomes, we will adjust p-values using bootstrapping (SAS Proc Multtest).

12.4 If this study has undergone scientific or scholarly review, please indicate which entity performed the review:

- Cancer Center Protocol Review Committee (PRC) (Full approval is required prior to final CHR approval for cancer-related protocols.)
- CTSI Clinical Research Center (CRC) advisory committee
- Departmental scientific review
- Other:

Specify **Other**:

Department of Veterans Affairs; SFVA R&D Committee

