14.0 Sample Size and Eligibility

14.1 Number of subjects that will be enrolled at UCSF and affiliated institutions:

120

14.2 Total number of subjects that will be enrolled at all sites (Help Text updated 9/13):

120

14.3 Estimated number of people that you will need to consent and screen here (but not necessarily enroll) to get the needed subjects:

218

14.4 Explain how and why the number of subjects was chosen (Help Text updated 9/13):

Although our primary analytic approach will be mixed effects linear regression models using a waitlist design, sample size estimates and power calculations are based on the simpler (and more conservative) situation of a repeated measures design with 1 pre and 2 post measures using effect size estimates from our pilot study, correlation between measures of 0.75 (based on our pilot data) and estimated alpha=0.03 (to account for multiple comparisons for our three co-primary outcomes). Sample size estimates at 80% power ranged from n=12/group to n=59/group depending on the effect size. Conversely, power estimates using a sample size of 60/group ranged from 81% to 100%. Power ranged from 71% to 100% for all outcomes even with 20% attrition. We estimate that we will need to contact and screen 218 potential study participants in order to enroll our target sample of 120 based on our pilot study response rate of 55%.

Sample Size and Power Estimates	Effect Size	Sample size, 80% Power	Power, N=60/ Group	Power, 20% Attrition
Co-Primary Outcomes				
Cognitive function (ADAS-cog)	0.76	12	1.00	1.00
Physical performance (SPPB)	0.34	59	0.81	0.71
Quality of life (QOL-AD)	0.83	10	1.00	1.00
Secondary Outcomes				
Caregiver burden (CBI)	0.49	29	0.97	0.92

14.5 * Eligible age range(s):

- 0-6 years
- 7-12 years
- 13-17 years
- 18+ years

14.6 Inclusion criteria:

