Screening (telephone, LAR/CG). Legally authorized representatives (LARs) of potential participants who have expressed interest in being contacted will be screened for eligibility over the telephone. Basic demographic and medical history information also will be collected after obtaining verbal consent. This information will be collected during screening in order to compare characteristics of those who choose to participate or not to assess for potential selection biases. Those who are eligible and interested will then be scheduled for an in-person consent visit. LARs may also serve as the study caregiver or may designate someone else (e.g., other family member, paid caregiver) to play this role. If an alternate study caregiver is designated, they will be screened and consented separately or consented with the LAR and potential participant if possible.

Consent Visit (in person, participant and LAR together). Similar to our pilot study, informed consent will be obtained with the participant and LAR together at a location of their choosing (e.g., home, SFVA, adult day center). Detailed consent procedures are provided in the Informed Consent section. In addition, the Montreal Cognitive Assessment (MoCA) will be administered to participants to measure global cognitive function. The MOCA is often used in clinical settings and will be used as a descriptive measure for clinical audiences to characterize dementia severity and also in exploratory analyses to determine whether baseline cognitive status acts as a confounder or effect modifier of the effects of PLIÉ. If an alternate CG is designated, they may be consented with the primary participant or at another time and place.

Baseline Assessment (with participants and caregivers separately). The baseline assessment may be performed immediately after the consent visit or scheduled for a later date. Participants and caregivers will provide data separately so that their answers do not influence each other. Participants will be directly assessed by research staff while caregivers will be provided with self-administered forms when feasible or may complete the assessment in person, by phone or mail-in.

Baseline Assessments in Participants

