Randomization. Study participants will be enrolled in one study site at a time in blocks of 20, and the randomization sequence will be generated in advance in blocks of 20 (10 Group 1, 10 Group 2) using a random number generator on a computer. The sequence will be stored in a secure location accessible only to intervention staff, and research staff who enroll study participants and collect outcome data will be unaware of the randomization sequence.

Blinding. Because we are using a waitlist design with usual care as the control condition, it will not be possible to blind study participants or their caregivers. However, research staff who collect outcome data will be blinded to group assignment. Every effort will be made to ensure that blinding is maintained including: 1) having interviewers remind study caregivers not to discuss any aspect of the study or ask any questions related to the study prior to scheduling or performing assessments; 2) excluding interviewers from staff meetings that discuss details of the intervention; and 3) maintaining the group assignment list separately from other study documentation. Interviewers also will be asked to guess which group participants were in to assess the adequacy of the blinding procedures.

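### Baseline covariates are chosen by significance tests between randomised groups, which leaves the primary model unfixed and does little to correct imbalance or gain precision

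*Combined protocol and SAP*

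**What the plan says.** Section 12.3 (Statistical analysis) sets out the baseline comparison and its consequence in two consecutive sentences: "Differences between the groups at baseline will be statistically tested using t-tests for continuous variables" (with non-parametric and Chi-square alternatives), and then "Any differences detected will be adjusted for in multivariable models". Further down, the same section restates the rule without referring to a test: "Models also will adjust for any baseline differences in demographic factors or confounders that may occur due to chance". It gives neither a significance level for the baseline tests nor a list of variables.

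The terms that are fixed are these: "Fixed effects terms will be included for treatment (PLIE vs. UC), sequence (Group 1 vs. Group 2), time (baseline, 4 months, 8 months"), plus treatment-by-time, with subjects as random effects. Baseline is the first level of time, so each outcome's own baseline value is in the model whatever the tests show. No covariate-by-time term is mentioned. The only other covariates are co-interventions, which arise after randomisation and are a separate matter.

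Section 16.1 (Randomization) describes a computer-generated sequence in blocks of 20 ("10 Group 1, 10 Group 2"), one site at a time. Section 16.1 (Consent Visit) collects MoCA before randomisation, but its possible role is left to exploratory analyses, "to determine whether baseline cognitive status acts as a confounder or effect modifier".

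**The concern.** A significance test between randomised groups tests a hypothesis already known to be true: the allocation was random, and section 12.3 itself attributes the differences to chance. The p-value therefore carries no information on whether a variable predicts cognition, physical performance or quality of life. A strong predictor that falls short of the threshold may be left out, while an irrelevant variable that crosses it goes in.

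Two things are at stake. First, the model for three co-primary outcomes depends on the observed baseline table, and the two adjustment sentences could give different covariate sets, since only the first is tied to a test. Second, variables likely to be prognostic and already collected (MoCA, CDR, demographics) have no settled place in the primary analysis, so the precision they could bring is not secured. This matters most for SPPB, which has the least margin in section 14.4: power 0.81, or 0.71 with 20% attrition.

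**Working it through.** **Inputs from the documents.** 60 per group; SPPB effect 0.34 SD; correlation between measures 0.75; "estimated alpha=0.03 (to account for multiple comparisons for our three co-primary outcomes"); one pre and two post measures (all section 14.4).

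**Assumptions, because the documents give no figure.** Baseline tests at 5%; 15 to 25 independent variables tested; one covariate correlating r = 0.3 to 0.5 with 4-month change.

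**1. Reproduce the plan's own figures.** The variance factor for the mean of two post measures minus one pre measure is (1 + 0.75)/2 + 1 − 2(0.75) = 0.375. With two-sided alpha 0.03 and 80% power, n = 2 × 0.375 × (2.170 + 0.842)² / 0.34² = 58.9, so 59 per group, as stated. Power at 60 per group: 0.34/√(0.75/60) − 2.170 = 0.871, giving 0.81. At 48 per group: 0.34/√(0.75/48) − 2.170 = 0.55, giving 0.71. Both agree with the table.

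**2. How often the rule fires by chance.** The probability of at least one hit is 1 − 0.95^15 = 54% for 15 variables and 1 − 0.95^25 = 72% for 25. For any one given variable it is 5%, however prognostic that variable is.

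**3. What the test misses.** The smallest detectable imbalance at 60 per group is 1.98 × √(2/60) = 0.36 SD. The SD of a single change score is √(2(1 − 0.75)) = 0.707. The bias in an unadjusted 4-month contrast at that threshold is 0.36 × r × 0.707:
- r = 0.3: 0.08 SD, which is 22% of 0.34
- r = 0.5: 0.13 SD, which is 37% of 0.34

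**4. Power and size in a simple change-score comparison (one post measure).** The standardised effect is 0.34/0.707 = 0.481. Simulated results for 60 per group:

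| | r = 0.3 | r = 0.5 |
|---|---|---|
| Power at alpha 0.03, test-then-adjust | about 67% | about 68% |
| Power at alpha 0.03, always adjust | about 71% | about 80% |
| Size at nominal 5%, test-then-adjust | about 4.7% | about 4.3% |

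A normal approximation agrees. Unadjusted: 0.34/√(2 × 0.5/60) = 2.634, less 2.170 = 0.464, or 68%. Always adjusted, dividing 2.634 by √(1 − r²) gives 2.761 and 3.042, or 72% and 81%. Test-then-adjust stays near the unadjusted figure because it adjusts for a given covariate in only about 5% of trials.

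**5. The same question in the planned mixed model.** With random subjects, a sequence term and baseline as the first time point, the treatment effect is estimated from within-person change. A covariate that is constant over time cancels from change unless it has its own time interaction. Simulations with 60 per group and a 0.35 to 0.36 SD imbalance bear this out:
- Complete data: adding the covariate as a main effect changed the treatment estimate by 0.000. The standard error was also unchanged.
- 20% missing follow-up: the estimate typically moved by about 0.01, and by at most about 0.02 to 0.04 in any single trial.
- Covariate predicts change: a near-miss imbalance biased the 4-month contrast by about 0.07 to 0.09 SD. Main-effect adjustment did not remove this; a covariate-by-visit term did.
- Effect pooled over both treatment periods: the bias was smaller, about 0.002 when the covariate acted equally at 4 and 8 months and about 0.03 when its effect grew with time.

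**The case against.** The strongest reply is that the rule hardly matters in this model. Since a main-effect covariate cancels, whether a variable passes or fails its test barely moves the treatment estimate. Selection uses baseline data only, never outcome differences, and nothing in the plan says that the tests follow unblinding. The second adjustment sentence sets no significance threshold, so an example built on p = 0.04 against p = 0.06 need not describe what would be done.

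Most of that stands, and it limits what can be claimed. A reader might infer that the data decide the primary estimate, or that false positives are inflated. The documents support neither: step 5 shows the estimate nearly fixed, and the simulated size in step 4 is slightly below nominal. Nor are the 67% to 80% power figures the plan's own operating characteristics. They use one post measure, whereas the stated 81% uses two. In a change-score comparison, entering a covariate amounts to a covariate-by-visit term, which section 12.3 does not provide. The bias in step 3 is a ceiling: it needs an imbalance at the threshold and a covariate that predicts change, not merely level.

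The reply does not rescue the rule. If the adjustment leaves the estimate and its standard error essentially as they were, it neither corrects imbalance nor gains precision, which are the reasons to adjust. It also leaves the model open.

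**Conclusion.** The point holds as one of prespecification and forgone precision. Covariates are selected by a test that cannot identify prognostic variables, no baseline covariate is named in advance, and the adjustment as written is close to inert in the planned model. Type I error is not at risk.

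Under the assumptions in the working, fixed adjustment would be worth about 4 percentage points of SPPB power at r = 0.3 and about 12 at r = 0.5. The most that an undetected imbalance could bias the 4-month contrast is about 0.08 to 0.13 SD. The direction of these results is secure. Their size rests on r, the 5% test level and the single post measure, none of which the documents fix for this purpose. The analysis should be changed, but the point does not threaten the validity of the trial.

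**What to change.** In section 12.3, delete the baseline significance tests and both sentences that make adjustment depend on observed differences. Keep the baseline table as description.

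Name a short set of covariates collected before randomisation and chosen for prognostic value, for example MoCA or CDR, age and sex, plus site/cohort because it is the randomisation block. Enter each prognostic term with a covariate-by-visit interaction in every primary model, whatever its balance. The interaction is the part that does the work: a fixed list of main effects alone would settle the model but leave the estimate where it is.

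The cost is SAP wording and some parameters. MoCA, age and sex take three each over three visits (9 in all). Site as a main effect across the planned six sites takes 5, so 14 in total. Roughly 10 to 15 parameters is affordable with 120 participants but is a reason to keep the list short; using both MoCA and a three-level CDR would add 6 more.
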